Study Protocol and Statistical Analysis Plan
For Research Project:
“Safety and Efficacy of Combining Intranasal Insulin & Acute Exercise”

clinicaltrials.gov # NCT04292535

conducted by [name], Ph.D.

March 19, 2021

“Safety and Efficacy of Combining Intranasal Insulin & Acute Exercise”

Abstract: To determine if physical activity engagement alters the dose-response profile and safety of administration of insulin into the intranasal mucosa. Using a randomized placebo controlled double-blind pre-posttest design, participants were randomly assigned to receive a dose of either 0, 20, 40, 60, 80, 100, or 120 IU of NovoLog insulin aspart prior to being randomized into participating in a 20 minute session of either moderate-intensity aerobic exercise or a passive control condition. The safety of the protocol was assessed using a symptom questionnaire assessing common symptoms of altered blood glucose and common side effects of intranasal insulin. The efficacy of the intranasal insulin for inducing alterations in cognition was assessed using both behavioral and neuroelectric measures.

Aims:

- 1) To provide a preliminary assessment of the safety profile of combining intranasal insulin with exercise; to ensure that undue risks are not incurred through combination therapeutic approaches.
- 2) To provide a preliminary assessment of the efficacy of combining intranasal insulin with exercise for enhancing inhibitory aspects of cognitive control and sustained attention alongside neuroelectric indices of attention.

Design: Double blind, placebo controlled Phase 2 clinical trial using serial stratification randomization accounting for biological sex. Participants were first allocated to a dose of intranasal insulin (0 [placebo], 20, 40, 60, 80, 100, 120 IU), then allocated to either exercise or control activity.

Study Population: Given the potential risk of combining exercise with intranasal insulin the present investigation utilized a sample of healthy, non-diabetic, fasted college-aged adults to limit the potential for a serious adverse event. The sample consisted of college aged young adults from the mid-Michigan, USA area.

Eligibility Criteria:

Criteria for inclusion: All individuals that agreed to participate were selected on a first come, first serve basis. No individual was turned down due to sex, race, or ethnicity. The following inclusion criteria exist for all participants:

- a. Participants must be over the age of 18.
- b. Participants must have normal or corrected-to-normal vision in order to complete the cognitive task.

Exclusion criteria: The following exclusion criteria exist for all participants:

- a. Lack of consent.
- b. Presence of any major neurological health issues, brain trauma, or concussion with loss of consciousness assessed through a health history and demographics questionnaire.
- c. Type I or Type II Diabetes.
- d. Self-reported pregnancy.
- e. Currently has any type of inflammation or blockage of the nasal passageways (i.e. allergies or a cold affecting the sinuses).
- f. Inability to engage in treadmill-based exercise.

Recruitment: Participants were recruited from the mid-Michigan community population via flyers and list-serve announcements.

Protocol: This investigation was approved by the Michigan State University Human Research Protection Program.

Screening Day (day 1): On the screening day of the testing protocol, following consenting to participate in this investigation; participants completed a brief health and history demographics questionnaire, a physical activity readiness questionnaire (Thomas et al., 1992), a medical screening questionnaire, the Wechsler Abbreviated Scale of Intelligence – 2nd Edition (WASI-II; (Wechsler, 2011), and a test of maximal oxygen uptake ($VO_2\text{max}$; using the same protocols as reported in (Chandler et al., 2019; Pontifex et al., 2016)). The medical screening questionnaire ensured that all participants were free of medication for high blood pressure, cholesterol, asthma, heart issues, depression/anxiety; and were not currently on any beta-blockers, sulfonamide antibiotics, corticosteroids, protease inhibitors, or Clonidine.

Participants who were eligible to continue in the study were then randomly assigned using a serial stratification approach accounting for biological sex to either an exercise [active experimental group] condition or sitting [control experimental group] condition. Within each condition; participants were subsequently randomly assigned using a serial stratification approach accounting for biological sex to receive a dose of either 0, 20, 40, 60, 80, 100, or 120 IU of fast acting insulin (Novolog Insulin Aspart 100 mg/mL) administered into the intranasal mucosa. Participants were instructed to refrain from exercise or caffeine intake, and too fast for at least 3 hours prior to participating in the second day of the testing protocol.

Assessment day (day 2): See Figure 1 for an overview of the assessment activities.

[figure not shown]

Figure 1. Diagram of experimental protocol.

Upon arriving to start the second day of testing, participants' blood glucose level was assessed via a glucometer (CVS Health Advanced Blood Glucose Meter, United States) to ensure that their blood glucose fell within the 70-115 mg/dL guideline to exercise safely. Following this, participants were outfitted with a polar heart rate monitor (Model H7, Polar Electro, Finland) to assess heart rate during the experimental condition and then were prepared for neuroelectric testing. Participants were subsequently seated in a sound-attenuated testing chamber approximately 1 m away from the computer monitor where they completed tests of inhibitory control and sustained attention while behavioral and neuroelectric measures were assessed. Once the pretest cognitive assessment was completed, participants were administered solution into their intranasal mucosa.

Using a double-blind, placebo-controlled approach; identical vials of saline solution and Novolog insulin aspart 100 mg/mL were obtained differentiated only by the color of the stopper top, and labeled as investigational drug A and investigational drug B. All participants were administered 6 doses of 0.2 mL of solution via the LMA MAD Nasal Intranasal Mucosal Atomization device into alternating nostrils with a total administration volume of 1.2 mL. The dose of intranasal insulin was controlled by varying the number of doses which contained saline relative to the doses which contained Novolog insulin aspart 100 mg/mL (see Figure 2). The experimenters were aware of the number of doses of investigational drug A and investigational drug B administered; but were unaware which solution or stopper top was associated with insulin or saline. Following administration of the solution, participants completed the sitting/exercise experimental conditions.

Figure 2. Illustration of the intranasal insulin dosing protocol.

Active Comparator: Passive Control. The sitting experimental condition consisted of a 20 min duration where participants sat in a chair (HR = 73.2 bpm [95% CI: 70.3 to 76.2]).

Intervention. The exercise experimental condition consisted of similar 20 min duration of exercise on a motor-driven treadmill at an intensity between 60 and 65% of maximum heart rate achieved during the test of maximal oxygen uptake (HR = 118.1 bpm [95% CI: 116.2 to 120.1]).

During both the sitting and exercise experimental conditions, participants watched an emotionally neutral video (minutes 65-85 from Wonders of the Universe (*Wonders of the Universe*, 2011)). Midway through the sitting and exercise experimental conditions and again 5 minutes following the completion of the experimental conditions, peripheral blood glucose was assessed via a glucometer. If peripheral blood glucose fell below 70 mg/dL, testing was immediately discontinued for all measures. Following the peripheral blood glucose assessment, participants again completed the tests of inhibitory control and sustained attention while behavioral and neuroelectric measures were assessed. Finally, upon completion of the cognitive assessments, participants completed a symptom survey which assessed potential side effects of intranasal insulin that participants might have experienced at any time during the experimental protocol and if participants were still experiencing those symptoms.

Measures:

Safety of Intranasal Insulin: The safety of intranasal insulin in combination with exercise was assessed by examining the incidence of participants reporting potential side effects of intranasal insulin (Schmid et al., 2018) at any time during the experimental protocol and the persistence of those symptoms. Additionally, the extent to which peripheral blood glucose was altered was also assessed via glucometer at the beginning of the session, during the middle of the exercise/sitting condition, and following the exercise/sitting condition

Inhibitory Control Task: Inhibitory control was assessed using a letter version of the Eriksen flanker task (Eriksen & Eriksen, 1974; McGowan et al., 2019), which is classified as a behavioral response selection construct of the inhibition/suppression focus and the performance monitoring focus of cognitive control according to the NIMH Research Domain Criteria (RDoC) classification system. Participants were instructed to attend to and to respond as accurately as possible to a centrally presented stimulus nested amid either congruous ('MMMMM') or incongruous ('NNMNN') flanking stimuli. Participants completed 80 practice trials at pretest followed by 160 trials grouped into two blocks of 80 trials, each consisting of equiprobable congruency and directionality; at each assessment period (160 trials pre-experimental condition and 160 trials post-experimental condition). For each block of trials, participants were presented with perceptually similar letter pairs (e.g., pretest block 1: M – N, pretest block 2: E – F, posttest block 1: I – T, posttest block 2: U – V) and were instructed to respond by pressing the button assigned to the letter presented in the middle of the flanking letters.

To ensure a high degree of task difficulty, at the midpoint of each block participants were given instructions to reverse the button-letter assignments (e.g., left button press for “M” through the first 40 trials and then right button press for “M” through the last 40 trials). Flanking letters were presented 300 ms prior to the onset of the target letter, and all five letters remained on the screen for a subsequent 100 ms (for a total stimulus duration of 400 ms) with a response window of 1000 ms and a variable inter-trial interval of 2300, 2400, 2500, 2600, or 2700 ms. All stimuli were 1.5 cm tall white block letters presented focally on a black background. Stimulus presentation and timing were controlled using PsychoPy 1.86 (Peirce, 2009). Reaction time was quantified within each congruency as the mean speed of responding following the onset of the stimulus only for correct trials. Response accuracy was quantified within each congruency as the proportion of correct responses relative to the number of trials administered.

Sustained Attention Task: Sustained attention was assessed using the rapid visual information processing task (Chandler et al., 2020; Neale et al., 2015) which is classified as a behavioral construct of attention according to the NIMH Research Domain Criteria (RDoC) classification system. Participants were presented with a series of single digits (1-9) in a box in the center of the screen at a rate of 100 digits/min and were instructed to make a button response with their right thumb as soon as they detected any of the three target sequences: ‘2-4-6,’ ‘3-5-7,’ or ‘4-6-8.’ To minimize working memory load, the three target sequences were presented on the bottom of the screen throughout the duration of the task. At pretest, participants completed a 1 min practice period prior to beginning the test trials which contained a series of 402 digits with 64 target sequences embedded. At posttest, participants completed another series of 402 digits with 64 target sequences embedded. Reaction time was quantified as the mean speed of responding following the presentation of the final digit of the target sequences only for correct sequence identifications. Response accuracy was quantified as the proportion of responses that correctly coincided with the 64 target sequences presented.

Neuroelectric Indices of Attention: During completion of the inhibitory control and sustained attention tasks, EEG activity was recorded from 32 electrode sites (Fpz, Fz, FCz, Cz, CPz, Pz, POz, Oz, F7/3/4/8, FT7/8, FC3/4, T7/8, C3/4, M1/2, CP3/4, TP7/8, P7/3/4/8, PO5/6) arranged in an extended montage based on the International 10-10 system (Chatrian, Lettich, & Nelson, 1985) using a Neuroscan Quik-Cap (Compumedics, Inc., Charlotte, NC). Recordings were referenced to averaged mastoids (M1, M2), with AFz serving as the ground electrode. In addition, electrodes were placed above and below the left orbit and on the outer canthus of both eyes to monitor electrooculographic (EOG) activity with a bipolar recording. Continuous data was digitized at a sampling rate of 2048 Hz and amplified 500 times with a DC to 70Hz filter using a Neuroscan Graef amplifier. The EEG data were then imported into EEGLAB (Delorme & Makeig, 2004), downsampled to 1024 Hz and prepared for temporal ICA decomposition. Data more than 2 s prior to the first event marker and 2 s after the final event marker were removed to restrict computation of ICA components to task-related activity. The continuous data was filtered using a 0.05 Hz high-pass 2nd order Butterworth IIR filter to remove slow drifts (Pontifex, Gwizdala, et al., 2017), and the mastoids electrodes were removed prior to ICA

decomposition. ICA decomposition was performed using the extended infomax algorithm to extract sub-Gaussian components using the default settings called in the MATLAB implementation of this function in EEGLAB with the block size heuristic ($\text{floor}[\sqrt{\text{EEG.pnts}/3}]$) drawn from MNE-Python (Gramfort et al., 2013). Following the ICA decomposition, the eyeblink artifact components were identified using the `icablinkmetrics` function (Pontifex, Miskovic, et al., 2017) and the EEG data was reconstructed without the eyeblink artifact.

Following removal of the eye blink components, stimulus-locked epochs were created for correct trials from -500 to 1,500 ms around the stimulus, baseline corrected using the -100 to 0 ms pre-stimulus period, and filtered using a zero phase shift low-pass filter at 30 Hz. Trials with artifact exceeding $\pm 100 \mu\text{V}$ were rejected. To ensure the integrity of the signal, stimulus-locked epochs were visually inspected blind to the experimental condition and dose prior to computing mean waveforms. Following visual inspection, the mean number of trials included in the waveforms was 112.0 [95% CI: 107.2 to 116.7] trials stimulus-locked to the congruent and incongruent trials (separately) of the Inhibitory Control task and 41.6 [95% CI: 40.1 to 43.2] trials stimulus-locked to the final stimulus of the target sequences of the Sustained Attention task.

Attention was indexed by the P3 ERP component. Attentional engagement was evaluated as the mean amplitude within a 50 ms interval surrounding the largest positive going peak within a 275 to 700 ms latency window following stimulus onset for the flanker task, and a 275 to 600 ms window for the RVIP task (Chandler et al., 2020; McGowan et al., 2019; Pontifex et al., 2015). Attentional processing speed was evaluated using ERP latency which was quantified as the time at which maximum peak amplitude occurred. Given the well-established nature of the P3 ERP component, analyses were conducted using a nine-channel region-of-interest approach centering around the topographic maxima of the P3 (i.e., the CP3/Z/4, P3/Z/4, PO5/Z/6 electrodes).

Aims Assessment:

- 1) *To provide a preliminary assessment of the safety profile of combining intranasal insulin with exercise; to ensure that undue risks are not incurred through combination therapeutic approaches.*

As the present investigation was a Phase II Clinical Trial, the research design is not sufficiently powered for hypothesis testing. Accordingly, this aim was satisfied by:

- A) Examining the frequency of participants reporting potential side effects of intranasal insulin at any time during the experimental protocol.
 - B) Examining the frequency of participants reporting potential side effects of intranasal insulin that persisted at the end of the experimental protocol.
 - C) Examining the frequency of study discontinuations due to violations of the safety thresholds (e.g., blood glucose outside the range of 70 to 150 mg/dL, feeling dizzy, or unable to safety continue the experimental protocol).
- 2) *To provide a preliminary assessment of the efficacy of combining intranasal insulin with exercise for enhancing inhibitory aspects of cognitive control and sustained attention alongside neuroelectric indices of attention.*

As the present investigation was a Phase II Clinical Trial, the research design is not sufficiently powered for hypothesis testing. Accordingly, this aim was satisfied by computing the within subject effect size for each participant as the standardized change relative to the pretest assessment using the within-subject (d_{rm}) variance correction for Cohen's d (Lakens, 2013). To ensure the integrity of the effect size estimates, within-subject effect sizes exceeding 3 times the interquartile range were identified as outliers and removed from analysis. For each measure, within each experimental condition, the effect of intranasal insulin was corrected by subtracting the effect size observed for the 0 IU placebo group to isolate the effects of intranasal insulin. Preliminary assessments of the efficacy were thus quantified using:

- A) Effect size estimates with 95% confidence intervals for both control and exercise conditions collapsed across congruencies of the Flanker task to quantify the effects on **Behavioral Indices of Inhibitory Control**. Reaction time effects and response accuracy effects were separately extracted.
- B) Effect size estimates with 95% confidence intervals for both control and exercise conditions in response to the target trial of the Rapid Visual Information Processing task to quantify the effects on **Behavioral Indices of Sustained Attention**. Reaction time effects and response accuracy effects were separately extracted.

- C) Effect size estimates with 95% confidence intervals for both control and exercise conditions for P3 amplitude at the nine-channel region-of-interest to quantify the effects on **Neuroelectric Indices of Attentional Engagement**. Effects collapsed across congruencies of the Flanker task and effects for the target trial of the Rapid Visual Information Processing task were separately extracted.

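### Aim 1 safety rests on three frequencies with no confidence interval and no exercise-versus-sitting comparison, so it cannot show which risks remain possible or whether exercise changes them

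*Combined protocol and SAP*

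**What the plan says.** In the combined protocol and SAP, the Aims section opens Aim 1 with "To provide a preliminary assessment of the safety profile of combining intranasal insulin with exercise" and completes the sentence with "to ensure that undue risks are not incurred through combination therapeutic approaches". The wording is repeated under Aims Assessment. The Abstract puts the question comparatively: whether physical activity alters the dose-response profile and the safety of intranasal insulin.

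Under Aims Assessment, both aims carry the statement that "the research design is not sufficiently powered for hypothesis testing". Aim 1 is then described as satisfied by three items:

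- Any side effect (item A): "Examining the frequency of participants reporting potential side effects of intranasal insulin at any time during the experimental protocol"
- Persisting side effects (item B): the matching count for symptoms still present when the session ended.
- Safety discontinuations (item C): the count of participants stopped because a safety limit was crossed.

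No interval, acceptable-risk limit, tabulation level or between-condition comparison is given for any of them. The four Aim 2 items each call for "Effect size estimates with 95% confidence intervals for both control and exercise conditions", after the 0 IU effect has been subtracted within each activity condition.

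The Design section sets out seven dose levels and two activities. Neither a total nor a per-cell sample size appears anywhere.

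**The concern.** A frequency without an interval does not tell the reader which true risks are still compatible with the data. That matters most when events are few, and this aim speaks of ensuring that undue risk is absent. Lack of power for testing is a good reason to estimate with intervals. The plan follows that reasoning for Aim 2 and not for Aim 1.

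The safety question is also about the combination. Frequencies listed side by side do not estimate whether exercise changes the risk after dosing, and Aim 1 has no counterpart to the placebo correction used in Aim 2. At stake is what the trial can conclude on its first aim; the data themselves remain usable.

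**Working it through.** **Inputs from the documents.** Seven doses (Design) times two activities gives 7 × 2 = 14 cells, of which six per activity contain insulin. Aim 1 items A to C are frequencies only; Aim 2 items A to D have 95% intervals (Aims Assessment). No sample size, event rate or acceptable-risk limit is stated, so there is no plan figure to reproduce.

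**Assumptions.** Cell sizes of 6, 8, 12 and 20. The pooled size of 48 is six active-dose cells of 8 within one activity.

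**Step 1: what a single frequency leaves open.** For 0 events in n, the exact (Clopper-Pearson) two-sided 95% upper limit is 1 − 0.025^(1/n). The chance of seeing no events when the true risk is 10% is 0.9^n. Zero is only an illustration, so the exact interval for one event is shown as well.

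| n (assumed) | Upper limit, 0 events | Chance of 0 events if true risk is 10% | Exact 95% interval, 1 event |
|---|---|---|---|
| 6 | 45.9% | 53.1% | 0.4% to 64.1% |
| 8 | 36.9% | 43.0% | 0.3% to 52.7% |
| 12 | 26.5% | 28.2% | 0.2% to 38.5% |
| 20 | 16.8% | 12.2% | 0.1% to 24.9% |
| 48 (pooled) | 7.4% | 0.6% | 0.1% to 11.1% |

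**Step 2: size needed.** For zero events to exclude a risk p with a two-sided 95% interval, n must be at least ln(0.025)/ln(1 − p), rounded up. This gives 36 for p = 10% and 72 for p = 5%.

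**Step 3: the comparison.** Take 48 dosed and 8 placebo participants per activity, with no events anywhere. The Wilson upper limit for 0/n is 3.8415/(n + 3.8415), and the Newcombe interval for a difference of two zero proportions of equal n is plus or minus that value.

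- Dosed, exercise minus sitting: 3.8415/51.8415 = 0.074, so ±7.4 percentage points.
- 0 IU, exercise minus sitting: 3.8415/11.8415 = 0.324, so ±32.4 points.
- Difference between the two, combining the margins: √(0.074² + 0.324²) = 0.333, so ±33 points.

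The last line is the quantity closest to the combination question, and its width comes almost wholly from the 0 IU groups. The frequencies as planned would not reveal this.

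**The case against.** The aim calls itself preliminary and the plan says openly that it is not powered for testing. On that view, the clause about ensuring gives the motive for a first look and promises no conclusion. This stands in part: the hedge must be quoted whenever the clause is. It concerns testing, however, and does not tell a reader how much risk is left open.

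A reader might infer that the plan tabulates safety in 14 cells and would take a zero count as evidence of safety. The documents support neither step. Items A to C name no tabulation level, and no rule equates zero with safe. If the frequencies are pooled within activity, the relevant upper limit under the assumptions above is about 7%, well below the 17% to 46% for single cells. Every n here is assumed. The Abstract describes the questionnaire items as common symptoms, so zero counts may be untypical for A and B.

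Safety was also not left to counts alone. Glucose was measured at three times and the population was restricted to healthy adults. That is true, but Aim 1 lists no glucose summary, and neither feature replaces an interval.

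Finally, Aim 2 also reports by condition without an explicit exercise-minus-sitting contrast, so that omission is not peculiar to safety. This stands. It does not remove the need for the contrast where the Abstract asks whether activity alters safety.

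**Conclusion.** The point holds in a limited form and should be acted on. Aim 1 is reported through frequencies that have neither an interval nor an exercise-versus-sitting comparison, while every Aim 2 estimate has a 95% interval. Frequencies alone cannot show which risks remain compatible with the data or whether exercise changes them, so the wording about ensuring goes further than the planned analysis can.

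The stronger reading, that the plan would declare cells with no events safe, goes beyond the text. What the text supports is that nothing in Aim 1 limits how a low or zero frequency is interpreted.

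The size of the gap is conditional. It runs from an upper limit of 46% (n = 6) to 17% (n = 20) with no events in one cell, and is about 7% with 48 pooled. The facts about what Aim 1 and Aim 2 report do not depend on these assumed sizes.

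**What to change.** 1. Report each of items A to C with its denominator and a Clopper-Pearson 95% interval, by dose and activity and pooled over the active doses within each activity. State the number of participants per cell.
2. Report the exercise-minus-sitting risk difference with a 95% interval among dosed participants and, separately, in the 0 IU groups, and then the difference between these two. The 0 IU contrast is needed because exercise alone may produce symptoms such as dizziness; a contrast among dosed participants only cannot separate that from the effect of the combination. Label all three as descriptive estimates, and keep the by-dose table so that pooling does not hide risk at the higher doses.
3. Replace the clause about ensuring with wording such as: *to estimate the risk, and state the upper limit compatible with the data*. Keep the word preliminary.

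No new data and no change to trial conduct are needed. The cost is a few table columns, intervals that will look wide (widest for the difference between the two contrasts), and a more modest safety claim.

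### The unqualified double-blind label overstates experimenter masking: known A/B spray counts rule out placebo for 5 of the 6 insulin doses

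*Combined protocol and SAP*

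**What the plan says.** The combined protocol and SAP uses the double-blind label in three places. The Abstract has "Using a randomized placebo controlled double-blind pre-posttest design", the Design paragraph has "Double blind, placebo controlled Phase 2 clinical trial", and Assessment day (day 2) has "Using a double-blind, placebo-controlled approach". None of the three carries a qualification.

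Assessment day (day 2) then describes how the masking worked. Saline and insulin came in matching vials coded A and B. "All participants were administered 6 doses of 0.2 mL of solution", and "The dose of intranasal insulin was controlled by varying the number of doses which contained saline" relative to those containing insulin. On what staff knew, the text is open: "The experimenters were aware of the number of doses of investigational drug A and investigational drug B administered". It adds that the A/B code itself was hidden from them. It does not say what the counts reveal about dose.

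Under Aims Assessment, Aim 2, the effect seen at 0 IU is subtracted from the effect at each insulin dose, separately in the sitting and exercise conditions.

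**The concern.** Hiding the A/B code is not the same as hiding the treatment. When dose is set by mixing two coded solutions over a fixed number of sprays, the mix carries information even to someone who cannot decode the labels. Placebo contains no insulin, so it cannot be a mix.

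What is at stake is what the label covers. A reader of the Abstract or Design paragraph would assume that experimenters could not tell active from placebo at any dose. Active versus placebo is also the comparison on which every Aim 2 estimate rests. If that masking was absent for most doses, the trial should not claim it for them.

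**Working it through.** **Inputs**
- Dose levels: 0 (placebo), 20, 40, 60, 80, 100 and 120 IU, so seven levels, of which six contain insulin (Abstract; Design).
- Sprays: six of 0.2 mL for everyone (Assessment day). The plan's own total is reproduced: 6 × 0.2 mL = 1.2 mL.
- Two labels, A and B, one saline and one insulin. Experimenters knew the two counts but not the code (Assessment day).

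**Insulin per spray.** The top dose uses all six sprays, so 120 IU / 6 = 20 IU per insulin spray. Taking 0 to 6 insulin sprays then gives exactly the seven listed doses. This figure comes from the dose list, not from the stated concentration, which is given in mg/mL and cannot be converted to IU from the documents.

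**What a count reveals.** With *a* sprays of A and 6 − *a* of B, the dose is 20*a* IU if A is insulin and 20(6 − *a*) IU if B is insulin. An experimenter who does not know the code must allow both.

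| Count (either order) | Possible doses | Could be placebo? |
|---|---|---|
| 6 and 0 | 0 or 120 IU | Yes |
| 5 and 1 | 20 or 100 IU | No |
| 4 and 2 | 40 or 80 IU | No |
| 3 and 3 | 60 IU only | No |

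**Active versus placebo.** Zero is possible only for an unmixed count. Every participant on 20, 40, 60, 80 or 100 IU had a mixed count, so 5 of the 6 insulin doses can be recognised as active. This step needs only the knowledge that one label is insulin and the other saline.

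**Exact dose.** The 3/3 count gives 60 IU under either code, so one of the seven levels can be identified exactly. This step also needs knowledge of the dosing scheme.

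**Contrasts.** Aim 2 has six placebo-subtracted contrasts in each condition, or 6 × 2 = 12 per measure. Those involving a dose whose count excludes placebo number 5 in each condition, or 5 × 2 = 10 per measure. The other two are 120 versus 0 IU, one in each condition.

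**What stayed masked.** Swapping the code turns a dose *d* into 120 − *d*.
- The pairs 0/120, 20/100 and 40/80 share the same possible doses, so neither member of a pair can be named from its count.
- An unmixed count is either placebo or the top dose, so no placebo participant is identified for certain.
- The swap reverses the order of any two different doses. For example, 1A/5B against 2A/4B is 20 against 40 IU under one code and 100 against 80 IU under the other. Counts alone therefore never show who had more insulin.

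**The case against.** The strongest defence has three parts.

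*It is disclosed.* The plan says plainly what experimenters knew and did not know, in the same paragraph as one use of the label, and an abstract need not carry such detail. The disclosure is real and to the plan's credit. But it gives the counts without their consequence, and it pairs them with a reassurance about the code that does not hide active from placebo for five doses. The Abstract and Design paragraphs give no pointer to it.

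*The knowledge has little use.* This largely stands. The reference group is never identified for certain, and an expectation that more insulin has more effect has no direction to act on while the code is unknown. Counting every pair of dose levels that staff could tell apart would exaggerate the problem: of the 21 pairs, 15 do not involve 0 IU, the only reference used in Aim 2. Even so, a mixed count has no chance of being placebo and an unmixed count has some, so masking of active versus placebo was incomplete.

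*No outcome is shown to be affected.* This stands. A reader might infer that the results are biased, and the documents do not support that. The cognitive tasks are presented on a screen and scored from timed button presses. For side effects, "participants completed a symptom survey which assessed potential side effects of intranasal insulin". The EEG section states that epochs were inspected blind to condition and dose. A reader might next turn to the discontinuations in Aim 1C, some of which may involve judgement. The documents do not say who made those decisions or whether they knew the counts. Splitting the discontinuations by reason would not isolate staff judgement either, since dizziness is something the participant feels.

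**Conclusion.** The point holds as a matter of description. For experimenters, the unqualified label claims a property that the design lacks: active versus placebo was fully masked only for 120 IU against 0 IU. Five of the six insulin doses were recognisable as active, and so five of the six placebo-subtracted contrasts in each condition lack the masking that the label implies. These figures show what the label covers; they do not measure bias, and none is shown.

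Ruling out placebo rests only on the stated counts and on knowing that one label was insulin and the other saline. Identifying 60 IU also assumes that the experimenter knew the scheme. The masking that remained rests on the code staying unknown, as the plan states. No allocation ratio is assumed. *Recognisable* is meant literally: the documents do not show that anyone made the inference.

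Nor should a reader infer that participants were unmasked. Nothing in the text shows it. Equally, the text does not spell out what participants were told or could see, so the label should not be recast as a specific claim about them.

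**What to change.** 1. Qualify the label in the Abstract, in the Design paragraph, in Assessment day (day 2) and in any report. One possible wording is: *double-blind to the A/B code; experimenters not masked to spray counts*.
2. After the statement on counts in Assessment day (day 2), add one sentence: *A mixed A/B count excludes placebo and a 3/3 count corresponds to 60 IU; from the counts, 0 IU was masked only against 120 IU, 20 against 100 and 40 against 80, so full experimenter masking of active versus placebo is claimed only for 120 IU versus 0 IU.*

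The document is written in the past tense, so correcting the description is the step still open. It needs no new data and changes no analysis. The downside is a weaker blinding claim. In return, the text also records the masking that did hold.
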